Study Protocol and Statistical Analysis Plan

Title: Improvements in upper extremity function following intensive training are independent of corticospinal tract organization in children with unilateral spastic cerebral palsy: A clinical randomized trial.

NCT: 02918890

Date: 5/1/2014

Study Objectives

This study aims to test the hypothesis that improvements in upper extremity function following either constraint induced movement therapy (CIMT) or bimanual training depend on corticospinal tract (CST) laterality and type of training (unimanual vs. bimanual) in children with unilateral spastic cerebral palsy (USCP). Specifically, we predict that children with a maintained contralateral CST will respond equally to CIMT and bimanual training, while children with ipsilateral CST laterality will be less responsive to CIMT than bimanual training.

Study Design

All study procedures will be approved by the Institutional Review Boards of Teachers College, Columbia University, where the treatments will be conducted, the Burke Medical Research Institute, where TMS evaluations will be performed, and Weill Cornell Medicine, where magnetic resonance imaging (MRI) will be performed.

We will recruit participants from clinics in the NYC area, our website (<http://www.tc.edu/centers/cit/>), ClinicalTrials.gov (NCT02918890), and online support groups. We will obtain written informed consent and assent from children and their caregivers.

We will randomize participants to receive either 90 hours of CIMT or Hand-Arm Bimanual Intensive Training (HABIT) after they complete all baseline outcome measures. Block randomization will be implemented for each cohort of participants, with each cohort stratified by age, sex, baseline hand function and CST connectivity pattern as closely as possible. Randomization will occur offsite using concealed allocation to receive either CIMT or HABIT. Intervention will be delivered in a day-camp model for 6 hours/day over 15 days for a total of 90 hours.

The inclusion criteria will be: 1) ages 6 to 17 years, 2) diagnosed with USCP 3) capable of participating in a 15 day, 6 hours/day day camp while separated from caregiver(s), 4) capable of following directions regarding hand use and testing, 5) capable of communicating needs, 6) mainstreamed in age-appropriate school classroom, and 7) able to lift the more affected arm 15cm above a table surface and grasp light objects. The exclusion criteria will be: 1) unwillingness to comply with instructions or other behavioral issues making delivery of an intensive therapy infeasible, 2) health problems unassociated with hemiplegia, 3) visual impairment that could interfere with participation, 4) orthopedic surgery on the more affected hand within 1 year, 5) presence of metallic objects in the body, and 6) botulinum toxin in the more affected upper extremity within the past 6 months or intended treatment within the study period, 7) seizures after the age of 2 years, 8) family history of seizure disorders, 9) current medication use to lower the seizure threshold, 10) claustrophobia, or 11) pregnancy.

We aim to recruit 82 participants based on sample size calculations from results of the Assisting Hand Assessment (AHA) and Jebsen-Taylor Test of Hand Function (JTTHF) outcomes of a prior CIMT/HABIT randomized controlled trial and pilot data.

Methodology

Children will participate in an intensive hand training intervention using either one (CIMT) or both (HABIT) hands. During the intervention, children will be paired with a trained interventionist, with an interventionist:child ratio of at least 1:1. We will recruit and train physical and occupational therapists, graduate students in kinesiology/neuroscience, speech pathology, and psychology, and undergraduates to be interventionists. Interventionists will be supervised by experienced PT/Ots. Both the interventionists and supervisors will be blinded to CST connectivity patterns. Prior to the intervention, a training session will be conducted by the supervisors for standardization based on the established manual of procedures for CIMT and HABIT. Fidelity will be reinforced by supervisors during the day camp and daily post-camp meetings. Participants receiving CIMT and HABIT will be located in separate rooms, with each room being supervised by experienced PTs/OTs who will model and ensure uniformity of treatment. Each day, interventionists will attend team meetings to discuss the progress and needs of each child.

Participants will work one-on-one with their interventionist or in groups, and activities will be divided into whole and part task practice. Whole task practice involves sequencing successive movements within the context of activities (e.g., games, arts and crafts, goal training). The activities will be performed continuously for at least 15 to 20 minutes. Targeted movements and spatial and temporal coordination will be practiced within the context of completing the task. Part task practice will involve breaking down motor skills into smaller components and reinforcement of successive approximations of the desired behavior (e.g., card turning to promote forearm supination) while increasing repetitions and progressing skill requirements. This approach will also serve to increase treatment intensity by requiring as many repetitions as possible over repeated 30 second intervals (typically a minimum of 5 intervals).

Constraint-Induced Movement Therapy

CIMT will be modified to be child-focused, using a cotton sling fastened to the child's trunk with the distal end enclosed to prevent using the less affected arm or hand as an assist. The sling will be continuously worn throughout the intervention, and breaks of up to 30 minutes will be given as requested. To engage the child in the intervention and to maintain engagement, we will establish a list of fine motor and manipulative gross motor activities that elicit movement behaviors of interest that include a battery of age-appropriate, unimanual functional and play activities. Interventionists will select tasks based on which train the targeted hand impairments and the child's interest. Task difficulty will be progressed as children improved by requiring greater speed, accuracy, or movement repetition.

Hand-Arm Bimanual Intensive Therapy

We will establish a list of age-appropriate fine and gross motor activities that require use of both hands. Activities will be chosen by taking into consideration the role of the more affected upper extremity (UE) increasing in complexity from passive assist to active manipulator. Children will be asked to use the more affected UE in the same manner as that of the non-dominant limb of a typically developing child. Directions will be provided

to the child before the start of each task to avoid use of compensatory strategies, specifying how each hand will be used during the activity.

Outcome Measures

We will use several measures of hand function to capture different aspects of manual ability. All measures will be administered immediately before treatment (pre-test), within two days after (post-test), and 6 months after treatment (follow-up). Assessments will be administered by an experienced physical or occupational therapist who is blinded to the treatment allocation and CST connectivity of each child.

The primary outcome measures will be the Assisting Hand Assessment (AHA) and Jebsen-Taylor Test of Hand Function (JTTHF). The AHA will measure bimanual hand use, while the JTTHF will measure unimanual dexterity of the affected hand.

AHA: The AHA is a validated test for measuring bimanual hand use in children with UE impairments. The AHA measures the use of the more affected hand in bimanual activities during a play-like testing session. Sessions will be videotaped and scored off-site by a blinded evaluator. The AHA has excellent validity, reliability (0.97-0.99) and responsiveness to change. The AHA units will be used for the analysis. The smallest detectable difference (SDD) for AHA is an improvement of at least 5 units.

JTTHF: The JTTHF measures the time taken to complete six unimanual tasks, which include flipping cards, moving small objects, and lifting cans. The total score is the amount of time taken to complete all tasks. The test will be performed on both the more affected and less affected hands. The JTTHF is well-validated and has excellent reliability.

Several secondary outcome measures will also be used. The Box and Blocks Test (BBT) will measure unimanual dexterity. The Canadian Occupational Performance Measure (COPM) will measure caregiver perceptions of a child's performance of functional goals, and satisfaction with how well the child can perform the goal. The ABILHAND-Kids is a parent-report of child's manual ability. The Pediatric Evaluation of Disability Inventory (PEDI) will be used to measure functioning in the home environment.

BBT: The BBT measures how many blocks (2.5 cm³) an individual can move from one box, over a barrier, to an adjacent box in one minute. Both hands will be tested. The BBT is valid and reliable for children with CP.

COPM: The COPM is a structured interview in which the individuals are asked to identify up to five functional goals. In this study, parents will report their child's functional goals in terms of how they perform each goal (COPM-Performance), and how satisfied they are with the child's performance (COPM-Satisfaction). The same caregiver will be interviewed at all time points. A change of 2 or more points in each scale of COPM is considered a minimum clinically important difference (MCID). The COPM has been validated for parents of children with disabilities.

ABILHAND-Kids: The questionnaire measures the ability of a child to perform specific 21 daily tasks which require hand use, according to the parent's perspective. It has been validated for children with CP over the age of 6 and it is a reliable test.

PEDI: Caregivers will be interviewed to assess children's daily functioning using the PEDI, a valid/reliable test focusing on child's functioning in daily living activities at home. Children's functional skills (PEDI-FS) and caregiver assistance (PEDI-CA) in self-care will be assessed.

Determination of CST Laterality

We will determine CST laterality in two ways. 1) TMS (primary approach): We will determine which hemisphere evokes muscle activation of the affected hand when TMS is applied to the primary motor cortex (M1); 2) DTI (secondary approach): We will use DTI to visualize the affected CST only in children whose CST laterality cannot be determined with TMS. We have shown that DTI is an accurate surrogate measure of CST laterality.

Transcranial Magnetic Stimulation

Single-pulse transcranial magnetic stimulation (TMS) will be used to determine which hemisphere's M1 controls movement of the child's more affected hand. We will record EMG from the first dorsal interosseous (FDI) muscle in both hands. Skin will be cleaned with rubbing alcohol and a mild abrasive (NuPrep, Weaver and Company, Aurora, CO). Electrodes will be placed on the FDI muscle belly. Reference electrodes will be placed on the muscle tendon, and a ground electrode will be placed on the wrist styloid process. EMG will be recorded with Neuroconn hardware and software (Neuropax, Germany). The Neuroconn will receive a trigger input from the TMS stimulator, such that the relative timing of an EMG response to a stimulus can be measured and visualized. The EMG response to TMS is a motor evoked potential (MEP).

We will identify the spot at which a single TMS pulse evokes the strongest MEP in the affected FDI muscle (the motor "hotspot"). To identify the motor hotspot, single TMS pulses will be delivered to the child's scalp, starting approximately 4 cm from midline above the ear. The initial TMS stimulus intensity will be 50% stimulator output. If an MEP is not found, the coil position will be moved in 1cm increments to stimulate the scalp above motor cortex on both hemispheres. Stimulus intensity will be increased in 2-5% increments until an MEP is found. We will stimulate up to 80% stimulator output, because higher stimulation can be painful to participants. If we are unable to find an MEP in the motor strip, we will stimulate at 80% stimulator output at 50 points across frontal and parietal cortices in one hemisphere. If no MEP is found at any of these sites, we will classify that hemisphere as having no direct control of the movement of either upper extremity.

After the motor hotspot is found, the resting motor threshold (rMT) will be determined. The rMT is defined as the minimum stimulus intensity needed to evoke an MEP in the affected FDI in 6 of 10 trials. Stimuli will be delivered at a frequency <0.1Hz. If an MEP

is found after 6 of 10 pulses, the stimulus intensity will be lowered 2% until an MEP is no longer found in 6 of 10 trials.

We will then place a circular grid over the hemisphere, centered over the hotspot, using Brainsight. The grid will have a 10cm diameter, with five concentric rings, each gridpoint placed 1cm apart. The grid will be centered over the hotspot for that hemisphere. We will stimulate each site 1-3 times at 110% the participant's rMT to thoroughly search for all motor cortex representations of the upper extremities. Responses are sites at which a TMS stimulus evoked an MEP 50 μ V or larger. We will calculate the ratio between the number of responses in the more affected FDI obtained from the lesioned and contralesional hemispheres. This ratio is the laterality index (LI).

Participants will be categorized as having a contralateral CST connectivity pattern if the LI is between 0.9 and 1; i.e., 90% to 100% of the responses in the more affected hand come from the lesioned hemisphere. Participants will be categorized as having an ipsilateral CST connectivity pattern if the LI is between 0 and 0.1; i.e., 0% to 10% of the responses in the affected hand come from the lesioned hemisphere. Participants will be categorized as having a bilateral CST connectivity pattern if the LI is between 0.1 and 0.9.

Transcranial Magnetic Stimulation Analysis

The latency and peak-to-peak amplitude of each TMS pulse will be measured using a suite of custom-written MATLAB (Mathworks, Waltham, MA) scripts. If the latency of the MEP is longer than 40ms after the TMS pulse, that trial will be excluded from analysis. Additionally, if high levels ($>100\mu$ V) of background EMG activity are seen before the MEP, the trial will be excluded from analysis.

Magnetic Resonance Imaging

Each child will receive a structural MR scan (MP-RAGE, 3D, T1-weighted) and diffusion tensor imaging scan, without sedation prior to participation. The structural MRI will be used to co-register TMS stimulation targets with specific brain landmarks, using a frameless stereotaxic neuronavigation system (Brainsight Frameless, Rogue Research, Montreal, QC, Canada). For TMS localization, there is normal variability in brain topography relative to scalp landmarks. MR scans will be done on a Siemens Prisma MRI Scanner (Malvern, PA) in the Citigroup Biomedical Imaging Center (CBIC). Structural scans (165 slices) will be taken at a resolution of 256 x 256 px. The structural MRI will be used to identify the lesion type and extent, as well as to localize the TMS coil (i.e., neuronavigation). The DTI scan will be done during the same session as the structural MRI. For DTI, a 65-direction protocol will be used, 75 slices per direction at a resolution of 112 x 112 px each.

Diffusion Tensor Imaging Analysis

DT images for participants whose CST laterality cannot be determined with TMS due to excessively high threshold or safety reasons will be imported into DTI Studio (Johns Hopkins University) software for processing and analyses. This has been shown to be a reliable surrogate for TMS in determining CST laterality. Image series for each

participant will be screened for movement artifact, and slices showing artifact will be removed. Since images are obtained using 65 gradients, up to 30% of slices may be removed without compromising feasibility of tract reconstruction. Using DTI Studio, we will place region of interest seeds in the affected motor cortex and cerebral peduncle, and later in the unaffected motor cortex and cerebral peduncle. We will use tractography to find tracts that pass through both regions of interest. We will categorize each CST as present or absent. If there is a present CST on the affected side, the child will be categorized as having a contralateral CST. If there is not a CST present on the affected side, and a CST present on the other side, the child will be categorized as having an ipsilateral CST.

Statistical Analysis Plan

This will be an intention-to-treat study. If a child misses their 6 month follow-up assessment, we will impute their missing data based on the average change data for other participants in their subgroup. Statistical analyses will be performed using SPSS (IBM). A treatment (CIMT, HABIT) x CST connectivity pattern (contralateral, ipsilateral, bilateral) x test session (pre-, post-, 6 month) ANOVA with repeated measures on test session will be performed on all measures and Newman-Keuls post hoc tests will be performed where appropriate. Regression analyses will be done to determine predictors of outcomes. For children with a bilateral CST, correlations will be done between the LI and changes in outcome measures. Statistical significance will be considered at the $p<0.05$ level.

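### The title concludes that improvement is independent of CST organization, but the plan has no rule that could establish this, and the treatment x CST term is too imprecise to support it

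*Combined protocol and SAP*

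**What the plan says.** The title of the document reads as a finding: "Improvements in upper extremity function following intensive training are independent of corticospinal tract organization in children with unilateral spastic cerebral palsy". Study Objectives, directly below, states the hypothesis to be tested in the opposite direction: "improvements in upper extremity function following either constraint induced movement therapy (CIMT) or bimanual training depend on corticospinal tract (CST) laterality and type of training". It then makes two predictions. The first is that "children with a maintained contralateral CST will respond equally to CIMT and bimanual training"; the second is that children with an ipsilateral CST will respond less to CIMT than to bimanual training. Together these describe a treatment x CST interaction.

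The Statistical Analysis Plan section specifies a treatment x CST pattern x session repeated-measures ANOVA on all measures. It adds Newman-Keuls post hoc tests, regressions for predictors, and correlations with the laterality index in bilateral children. The one criterion is "Statistical significance will be considered at the $p<0.05$ level". There is no equivalence margin, confidence-interval rule or power statement for any CST term.

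Under Outcome Measures, "The smallest detectable difference (SDD) for AHA is an improvement of at least 5 units". That figure is not tied to any decision in the analysis.

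**The concern.** A non-significant test does not show that an effect is absent. If the CST x session and treatment x CST x session terms come out above 0.05, the plan gives no way to separate a CST effect that has been ruled out from one the trial was too small to see. The title nevertheless uses the wording of the first case.

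The title's claim compares CST patterns. It is not the prediction of equal response in contralateral children, which compares the two trainings within one pattern.

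CST pattern is the subject of the hypothesis, a stratification factor, and the reason for the TMS and DTI work. Readers could take independence to mean that CST pattern need not inform the choice between the two trainings. That inference depends on the treatment x CST difference, which this design estimates least precisely.

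**Working it through.** **The plan's own figure.** The sample-size statement is "We aim to recruit 82 participants based on sample size calculations", drawn from "outcomes of a prior CIMT/HABIT randomized controlled trial and pilot data". No effect size, SD, power or dropout rate is given, so 82 cannot be reproduced. With 41 per arm and two-sided 0.05, the standardised treatment difference detectable with 80% power is (1.96 + 0.84) x sqrt(2/41) = 0.62. With 90% power it is 0.72. Both concern the overall arm comparison, not any CST term.

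**Inputs.**
- From the documents: N = 82; two arms; three CST patterns; alpha 0.05; 5 AHA units as a reference size.
- Assumed: 1:1 allocation within each pattern; two-sided testing; contralateral/ipsilateral/bilateral splits of 28/27/27, 40/26/16 and 20/42/20; SD of AHA change of 5 or 8 units.
- Residual df = 82 - 6 cells = 76, so t(0.975) = 1.992.

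**Formulas**, for the contralateral-ipsilateral comparison of change, with pattern sizes n1 and n2:
- Pooled over arms: SE = SD x sqrt(1/n1 + 1/n2).
- Treatment x CST: each pattern is halved between arms, so SE = SD x sqrt(4/n1 + 4/n2), twice the pooled SE.
- 95% CI half-width = 1.992 x SE.
- Miss rate = P(|T| < 1.992), where T is noncentral t with 76 df and noncentrality 5/SE.

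**Example.** For 28/27/27 and SD 5, sqrt(1/28 + 1/27) = 0.2697. The pooled SE is 1.35 and its half-width 2.69. The treatment x CST SE is 2.70, its half-width 5.37 and its noncentrality 5/2.70 = 1.85, giving a miss rate of 55%.

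| Split | SD | Pooled half-width | Pooled: 5 units missed | Treatment x CST half-width | Treatment x CST: 5 units missed |
|---|---|---|---|---|---|
| 28/27/27 | 5 | 2.69 | 4.5% | 5.37 | 55% |
| 28/27/27 | 8 | 4.30 | 37% | 8.60 | 79% |
| 40/26/16 | 5 | 2.51 | 2.5% | 5.02 | 50% |
| 40/26/16 | 8 | 4.01 | 31% | 8.03 | 77% |
| 20/42/20 | 5 | 2.71 | 4.7% | 5.41 | 56% |
| 20/42/20 | 8 | 4.33 | 38% | 8.66 | 79% |

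**Reading the treatment x CST columns.** A non-significant result means that the interval contains zero. With a half-width of at least 5.0, at least one end must then lie at or beyond 5 units.

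**Reading the pooled columns.** An interval inside +/-5 units is possible if the estimate lies within 5 minus the half-width of zero, that is, within 2.49 units at best and 0.67 at worst. If the true difference is zero, the chance is about 2 x Phi((5 - half-width)/SE) - 1. This gives 91-95% at SD 5 and 24-38% at SD 8.

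**Sensitivity.** With no bilateral children (41/41) and SD 5, the treatment x CST half-width is 1.992 x 5 x sqrt(8/41) = 4.40, just inside 5, and a 5-unit difference is missed 39% of the time. An interval within +/-5 would then need an estimate within 0.6 units of zero. In the other direction, the 2-df test across three patterns is less sensitive than the single contrast. With the bilateral mean midway, it misses a 5-unit pooled difference 5-9% of the time at SD 5 and 42-48% at SD 8.

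No matching calculation is possible for JTTHF, because the documents give neither an SD nor a relevance threshold for it.

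**The case against.** A title is not an analysis rule. No section says that a non-significant term will be read as independence, the stated objective is to test dependence, and silence about confidence intervals does not forbid reporting them. This is fair as far as it goes. But the title heads the plan, contradicts its hypothesis, and has nothing in the analysis section to support it. The regressions and correlations would yield estimates, but they fall under the same 0.05 criterion.

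A reader might infer that a null result is likely for every CST term even when CST matters. That rests on an effect of 0.5 SD of change. A pooled difference of that size is missed 50-56% of the time, and a treatment x CST difference 83-85%. At the assumed SDs, however, 0.5 SD is only 2.5-4 AHA units, below the only threshold the documents give. At 5 units the pooled term performs much better, so the stronger reading is not supported for it.

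A reader might also infer that the plan was written with the results in hand. The documents do not say when the title was added, so this is not supported either.

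Three further objections stand as limits. The splits and SDs are assumptions. The miss rates are for one test on one outcome, and a dependence that affects several measures would be missed on all of them less often, unless those outcomes are perfectly correlated. And 5 units is given as a threshold for improvement; nothing in Outcome Measures makes it a margin for differences between groups, still less for a difference of differences.

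**Conclusion.** The point holds in two parts. First, without any numerical assumption: the title states a conclusion opposite to the hypothesis, and the plan's only criterion could deliver it solely through non-significance. Second, under the stated assumptions, the gap has real consequences for treatment x CST. A 5-unit AHA difference between contralateral and ipsilateral children in the CIMT-HABIT effect would be missed about half to four-fifths of the time, and a null result could not exclude it. This second part would soften if almost no child were bilateral and the SD of change were near 5 units or lower.

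The pooled CST difference should not be described in the same terms. Depending on the SD, a bounded statement about it on AHA may be attainable with 82 children.

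**What to change.** Use a neutral title, for example one asking whether improvement after intensive training depends on CST organization. Add to the Statistical Analysis Plan:

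> For AHA and JTTHF, differences between CST patterns in change, and the treatment x CST difference, will be reported with 95% confidence intervals. A non-significant CST term will not be reported as independence. It will be reported as inconclusive unless the interval excludes a margin justified in advance.

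The 5-unit AHA figure is one candidate margin, but the sponsor must justify applying it to group differences. A JTTHF margin needs its own justification, fixed before unmasking. If results are already known, the intervals and the inconclusive wording can still be used, with any margin labelled post hoc. It would also help to state that the treatment x CST comparison is unlikely to support an independence claim at this sample size.

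The cost is wording and a few intervals from the planned model, with no new participants or data. The downside is that a null result must be reported more modestly.

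### The plan predicts that contralateral-CST children respond equally to CIMT and HABIT, but no planned analysis can support that or tell it from an inconclusive result

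*Combined protocol and SAP*

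**What the plan says.** Study Objectives gives a general hypothesis, that improvement depends on CST laterality and on type of training, and then two specific predictions. For one subgroup it predicts no difference: "children with a maintained contralateral CST will respond equally to CIMT and bimanual training". For the other it predicts a directional difference: "children with ipsilateral CST laterality will be less responsive to CIMT than bimanual training".

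The Statistical Analysis Plan section specifies "A treatment (CIMT, HABIT) x CST connectivity pattern (contralateral, ipsilateral, bilateral) x test session (pre-, post-, 6 month) ANOVA" with repeated measures on session, applied to all measures. It adds that "Newman-Keuls post hoc tests will be performed where appropriate". It also plans regressions to find predictors of outcome and, in bilateral children only, correlations of the laterality index with change. The one decision rule is "Statistical significance will be considered at the $p<0.05$ level".

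The Outcome Measures section names AHA and JTTHF as the primary outcomes and gives 5 units as the smallest detectable difference (SDD) for AHA. It presents that figure as a property of the measure and does not tie it to any comparison between arms.

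**The concern.** The two specific predictions need different kinds of evidence. A difference test can support the ipsilateral one. For the contralateral one, the same test can only reject equality or fail to reject it. Failing to reject may mean that the treatments are close, or that the subgroup was too small to tell.

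The plan gives no interval, margin or reading rule that would separate these two outcomes. If the contralateral comparison is not significant, the write-up has no pre-specified basis for saying whether that prediction was borne out, and reading p>0.05 as confirmation would be an error.

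**Working it through.** **1. Each planned analysis against the contralateral prediction**

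- Treatment x CST x session term: shows whether the treatment effect on change varies with CST pattern. A significant result does not show that the effect is near zero in contralateral children.
- Newman-Keuls tests: difference tests. No contralateral CIMT-HABIT comparison is named, and a non-significant one is not evidence of equality.
- Regression: tests of association, with no equality criterion attached.
- Laterality index correlations: bilateral children only, so not relevant here.

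This step needs no assumed numbers.

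**2. The plan's own figure**

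The target of 82 (Study Design) cannot be reproduced, because effect size, SD, power and CST mix are not given. Read as a two-arm difference test with 41 per arm, 80% power and two-sided 0.05, it would imply a standardised difference of (1.96 + 0.84) x sqrt(2/41) = 0.62. That is a whole-arm figure and says nothing about precision in contralateral children.

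**3. Illustration: inputs**

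- n per arm in contralateral children (assumed, with 1:1 allocation): 14, from one third of 82 (82/6 = 13.7); 20, from about one half (82/4 = 20.5).
- SD of pre-post AHA change (assumed): 4, 5, 6 or 8 units.
- True difference: 5 AHA units. This borrows the SDD as a yardstick only.
- Two-sided 0.05 (sidedness is not stated), single pre-post change, two-sample t with 2n-2 df.

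**4. Formulas**

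- SE = SD x sqrt(2/n).
- P(p>0.05) = P(|T| < t(0.975, 2n-2)), with T noncentral t and noncentrality 5/SE. The critical value is 2.056 for n = 14 and 2.024 for n = 20.
- 95% half-width = critical value x SE, with the sample SD at its assumed value.
- Chance of meeting an illustrative equality rule at true difference 0 = P(|D| + t(0.95, 2n-2) x estimated SE < 5), integrated over the sample SD (90% CI within +/-5).

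Example, n = 14 and SD 6: SE = 6 x sqrt(2/14) = 2.27; noncentrality = 5/2.27 = 2.20; P(p>0.05) = 44%.

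**5. Results**

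| n per arm | SD | SE | 95% half-width | p>0.05 at true 5 units | 90% CI within +/-5 at true 0 |
|---|---|---|---|---|---|
| 14 | 4 | 1.51 | 3.1 | 11% | 88% |
| 14 | 5 | 1.89 | 3.9 | 28% | 65% |
| 14 | 6 | 2.27 | 4.7 | 44% | 39% |
| 14 | 8 | 3.02 | 6.2 | 64% | 6% |
| 20 | 4 | 1.26 | 2.6 | 3% | 97% |
| 20 | 5 | 1.58 | 3.2 | 13% | 86% |
| 20 | 6 | 1.90 | 3.8 | 27% | 65% |
| 20 | 8 | 2.53 | 5.1 | 51% | 24% |

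**6. Why p>0.05 alone is ambiguous**

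Take n = 14 and SD 5. An observed difference of 0 gives an interval of -3.9 to 3.9, which excludes 5 units. An observed difference of 3.5 gives -0.4 to 7.4, which does not. Both are non-significant, and the plan's only rule labels them alike.

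**The case against.** The best defence is that the study sets out to test dependence on laterality, and the three-way term does that. Equal response in contralateral children is one half of an interaction pattern, and it can be refuted as planned. Nowhere does the plan say that p>0.05 will be read as equality, and formal equivalence is a lot to ask of a mechanistic subgroup prediction.

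Much of this stands. A reader might infer that the plan cannot test its main hypothesis, or that it commits the error of accepting the null. The documents support neither: the first is contradicted by the ANOVA, and the second would be a fault of a later write-up. What remains is that a prediction stated specifically has no planned route to support.

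A reader might also infer that a non-significant result is always compatible with a 5-unit difference. That depends on the assumed SD and subgroup size. With 14 per arm and SD 5 or 6, a near-zero estimate would exclude 5 units. At SD 4 with 20 per arm, a true 5-unit difference is missed in only about 3% of trials.

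Finally, the title's wording, "Improvements in upper extremity function following intensive training are independent of corticospinal tract organization", may tempt a reader to add a second no-difference claim without a criterion. It runs against the hypothesis in Study Objectives, so it is not a prediction that this plan sets out to test, and the point does not rely on it.

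**Conclusion.** The concern holds for the contralateral prediction only. The plan can refute equal response in contralateral children but cannot support it, or distinguish it from an inconclusive result. This follows from the text and does not depend on any assumed figure.

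Its practical size is uncertain, because the documents give no SD, effect size or CST mix. Over the assumed range, the chance that a true 5-unit AHA difference goes undetected runs from about 3% (20 per arm, SD 4) to 64% (14 per arm, SD 8). The 5-unit yardstick is a measurement benchmark and not a between-arm margin, and no comparable figure can be given for JTTHF. The randomised comparison itself remains valid. The gap is worth closing because it determines what the trial can say about one of its two specific predictions.

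**What to change.** Keep the planned ANOVA and add to the SAP, before unblinding:

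- For AHA and JTTHF, at one named timepoint, the CIMT-HABIT difference in change from pre-test with a confidence interval in contralateral children, and likewise in ipsilateral children. The timepoint should not be an average over visits. A 5-unit post-test difference that halves by 6 months averages (5 + 2.5)/2 = 3.75, so averaging can hide it.
- A statement that a non-significant contralateral comparison will not be read as equal and will be reported as an estimate with its interval.
- If an equality claim is wanted, a rule that it is made only when the interval, at a stated level, lies within a margin justified before unblinding. The AHA SDD is not automatically that margin. JTTHF needs its own margin, or no equality claim should be made for it.

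The cost is SAP wording, plus the work of justifying a margin if one is used. No extra children or assessments are needed. The downside is that the contralateral result may often be inconclusive: with the illustrative +/-5 rule and 14 per arm, truly equal treatments would be called equal in about 88, 65, 39 or 6% of trials at SD 4, 5, 6 or 8.
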